1.33.3 Analysis of the Secondary Endpoint(s)

There are 2 sets of key secondary endpoints. These analyses are not dependent on findings of the primary endpoint. They will be calculated as changes from baseline to 16-week visit in the ITT dataset:

1. Changes in BMI and fat mass after 16 weeks of liraglutide.
2. Comparison of changes in BMI and fat mass after 16 weeks of liraglutide in participants who had a poor initial response to SG (<20% BMI reduction at BMI nadir) vs. those with a typical post-SG weight loss ($\geq 20\%$ BMI reduction at BMI nadir)

For these analyses, last observation carried forward (LOCF) imputation will be used for missing data. The sample is too small to use any other statistical imputation method accurately. A sensitivity analysis using baseline observation carried forward (BOCF) will also be conducted.

Changes in BMI and fat mass after 16 weeks of liraglutide will be evaluated using paired t-tests of baseline versus 16-week values. Data will be transformed as necessary to meet statistical assumptions of normality.

Comparisons between those who had a poor versus typical post-SG weight loss will be conducted with ANCOVAs with change (16-week minus baseline value) as the dependent factor; group (poor vs. typical weight loss) as the independent factor; and sex, race, age, and height tested as potential covariates.

Tertiary endpoints will be evaluated using similar approaches. For the secretome analysis, paired statistical tests will be applied to each analyte (using parametric or nonparametric statistical approaches as required by the data) to find significant changes in secretome components. The Benjamini-Hochberg procedure will be used to determine the false discovery rate for multiple comparisons.

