1.8 SCIENTIFIC RATIONALE FOR STUDY DESIGN

We propose a pilot open-label treatment study to estimate effect sizes and identify potential responders for a subsequent larger randomized, double-blind, placebo-controlled trial. Data will be compared for patients with poor weight loss response to SG ($< 20\%$ BMI reduction) vs. those with typical post-SG weight loss ($> 20\%$ BMI reduction) but who have persistent obesity (BMI ≥ 30 kg/m² or $\geq 95^{\text{th}}$ percentile for age and sex) 1 year or more after SG. These data will allow determination of the sample size for a future fully powered randomized controlled trial.

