1.30 STATISTICAL HYPOTHESIS

- Primary Endpoint:

The Primary Endpoint is estimation of required sample size for a later RCT through calculation of effect size for change in body mass index (BMI) from baseline to 16 weeks of liraglutide. The hypothesis is: The data will be sufficient to calculate the effect size for change in BMI from baseline to 16 weeks for a 2-group experiment (placebo versus liraglutide).

- Secondary Endpoint(s):

There are 3 sets of key secondary endpoints:

- A. Changes in BMI and fat mass after 16 weeks of liraglutide.
- B. Comparison of changes in BMI and fat mass after 16 weeks liraglutide in participants who had a poor initial response to SG (<20% BMI reduction at BMI nadir) vs. those with a typical post-SG weight loss ($\geq 20\%$ BMI reduction at BMI nadir)
- C. Tolerability and safety of 3.0 mg Liraglutide

Statistical hypothesis A: there will be a statistically significant decrease in BMI and fat mass after 16 weeks of liraglutide.

Statistical hypothesis B: there will be a statistically significant greater decrease in BMI and fat mass after 16 weeks of liraglutide in participants in who had a typical post-SG weight loss vs. those who had a poor initial response to SG.

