1.31 SAMPLE SIZE DETERMINATION

As this is a pilot investigation to determine the sample size of a fully powered investigation, no formal sample size determination is necessary. That said, the study is powered such that it might be able to detect a moderate-to-large difference from treatment. A recent randomized, double-blind, placebo-controlled phase 3 trial of liraglutide for adolescents (age 12 to <18 years) with obesity ($BMI \geq 30 \text{ kg/m}^2$ and $\geq 95^{\text{th}}$ percentile for age and sex) [32] reported a -1.39 kg/m^2 ($SE=0.31$, $n=125$) difference over 1 year of liraglutide treatment. If that effect size is replicated and if a similar SD (3.46) is found in the present study, we estimate that a total sample size of 40 subjects will have 80% power (β) to detect a -1.39 kg/m^2 difference in BMI (effect size = -

Abbreviated Title: Liraglutide in Teens Post-SG

Version Date: 1/30/23

0.4017) at level of significance of 0.05 (1-sided, as we are interested only in BMI loss). See **Table 2**.

t-test - Means: Difference between two dependent means (matched pairs) Tails = 1, $\alpha = 0.05$, Effect size dz = 0.4

[figure not shown]

Table 2, drawn using data obtained using G-Power 3.1.9.2 [90, 91]

We anticipate that virtually all participants who sign consent and are screened will qualify and agree to enroll. We will therefore attempt to recruit and screen in person no more than 50 adolescents, among whom no more than 43 will be treated with liraglutide in hopes of having 40 who complete the study. Based on prior studies in adolescents using liraglutide, we anticipate few dropouts or withdrawals by week 16. In Kelly et al's study of adolescents [32], 119/125 (95%) of those treated with liraglutide remained on-treatment at week 16.

As a pilot investigation, there is no assumption that there will be adequate power for any of the secondary outcomes investigated. We will, however, be able to use the data to determine power in a future randomized controlled trial for these outcomes.

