1.33 STATISTICAL ANALYSES

1.33.1 General Approach

Tabulations will be produced for appropriate demographic, baseline, efficacy, and safety parameters. For categorical variables, summary tabulations of the number and percentage of subjects within each category of the parameter will be presented. For continuous variables, the number of subjects (N), mean, median, standard deviation (SD), minimum, and maximum values will be presented.

Formal statistical hypothesis testing will be performed on endpoints with testing conducted at the 1-sided, 5% level of significance. Summary statistics will be presented, as well as confidence intervals (Cis), as described in the sections below. Trial success will be based on a p-value <0.05.

Covariates to be modeled are pre-specified in the sections below. Results of statistical procedures for efficacy outcomes involving covariates will be presented as adjusted means (least-squares means) with standard errors.

Checks of assumptions (e.g., normality) underlying statistical procedures will be performed and corrective procedures will be applied. It is expected that log transformation will be used for the primary outcome and most secondary outcomes. Percentage data will be arcsin (square root (value)) transformed for analysis.

Unless otherwise noted, all statistical analyses will be performed using SPSS statistical software Version 25 (IBM Corp, Armonk, NY) or higher.

Subject disposition will be tabulated and include the number screened, the number randomized, the number treated in total, the number dosed with liraglutide, the number in each subject population for analysis, and the number who withdrew prior to completing the study and reason(s) for withdrawal.

A by-subject data listing of study completion information including the reason for premature study withdrawal, if applicable, will be made available. Subject disposition will include patients in the Screening Analysis Dataset.

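### Surgical response is analysed only as a 20% cut; a prespecified continuous-term model beside the group comparison would use the same data more fully

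*Combined protocol and SAP*

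**What the plan says.** Section 1.33.3 (Analysis of the Secondary Endpoint(s)) sets a comparison of "participants who had a poor initial response to SG (<20% BMI reduction at BMI nadir) vs. those with a typical post-SG weight loss", the latter meaning a reduction of at least 20%. The model is an ANCOVA on the change from baseline to week 16, with "group (poor vs. typical weight loss) as the independent factor; and sex, race, age, and height tested as potential covariates". Surgical response therefore enters only as a two-level factor. No section plans an analysis of the percentage itself.

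Section 1.30 attaches a directional hypothesis, labelled B, which predicts that "there will be a statistically significant greater decrease in BMI and fat mass after 16 weeks of liraglutide in participants in who had a typical" response to surgery, compared with poor responders. Section 1.33.1 has "testing conducted at the 1-sided, 5% level of significance".

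Section 1.8 explains the purpose. The pilot is to estimate effect sizes and find likely responders for a later randomised trial, and "Data will be compared for patients with poor weight loss response to SG" against those with a typical response.

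On power, Section 1.31 states that "there is no assumption that there will be adequate power for any of the secondary outcomes investigated". Its one calculation for this trial concerns the overall paired change in BMI. The documents give no expected split between the two groups, no SD for percentage BMI reduction at nadir and no power figure for this comparison.

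**The concern.** Classifying a participant requires the percentage reduction at nadir. The planned analysis then keeps only which side of 20% it falls on. A 19% and a 21% responder are treated as different, and a 21% and a 40% responder as the same. If benefit from liraglutide varies gradually with surgical response, the contrast uses only part of what was collected, in a sample too small to make up the loss.

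The split is also left to chance. Section 1.7 mentions stratified randomisation by surgical response, but the trial has one arm and Section 1.19 says randomisation does not apply. No section sets an enrolment target per group, and the more uneven the groups, the more a cut costs.

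At stake is the precision of the comparison meant to show who is likely to respond. The primary endpoint and the overall change in BMI are unaffected.

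**Working it through.** **Inputs from the documents.** About 40 completers hoped for, SD of BMI change 3.46 kg/m² and assumed overall change 1.39 kg/m² (Section 1.31); one-sided 5% (Section 1.33.1); cut at 20% (Section 1.33.3).

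**Assumptions not in the documents.** The share p below 20%; a roughly normal distribution of percentage BMI reduction; a linear relation with the week-16 change; and, for power, the correlation between the two.

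**1. The plan's own figure.** Section 1.31 says that "a total sample size of 40 subjects will have 80% power", "if a similar SD (3.46) is found in the present study". The effect size is 1.39/3.46 = 0.4017. A paired t-test with n = 40 at one-sided 0.05 (noncentral t) has power 0.803. The SD agrees with the cited standard error: 0.31 × √125 = 3.47. The figure reproduces, but it concerns the overall paired change and not the group comparison.

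**2. Information kept by the cut.** For a normal predictor with a linear effect, the efficiency of the two-group form relative to the slope is φ(z_p)² / [p(1 − p)].

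| Share below 20% | Efficiency | Information lost | Effective n out of 40 |
|---|---|---|---|
| 50% | 0.637 | 36% | 25.5 |
| 30% | 0.576 | 42% | 23.0 |
| 20% | 0.490 | 51% | 19.6 |
| 10% | 0.342 | 66% | 13.7 |

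This ratio does not depend on the outcome SD, so under the same assumptions it applies to fat mass as well as BMI.

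**3. Detectable BMI difference with the cut.** By the normal approximation, (1.645 + 0.842) × 3.46 × √(1/n₁ + 1/n₂):
- 20 v 20: 2.487 × 3.46 × 0.316 = 2.72 kg/m²
- 8 v 32: 2.487 × 3.46 × 0.395 = 3.40 kg/m²

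The noncentral t gives 2.77 (20 v 20), 3.02 (12 v 28) and 3.46 (8 v 32).

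**4. Equivalent contrast for the slope.** Multiplying by the square root of the efficiency gives the underlying group difference that the slope test could detect:
- 50:50: 2.72 × √0.637 = 2.17 kg/m²
- 20:80: 3.40 × √0.490 = 2.38 kg/m²

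Against the assumed overall change of 1.39, the cut needs 2.72/1.39 = 2.0 to 3.46/1.39 = 2.5 times that amount. The slope needs 2.17/1.39 = 1.6 to 2.38/1.39 = 1.7 times.

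**5. Power by simulation.** n = 40, one-sided 0.05, no covariates, 40,000 replicates per setting:

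| Assumed correlation | Continuous | Cut 50:50 | Cut 30:70 | Cut 20:80 |
|---|---|---|---|---|
| 0.20 | about 0.35 | 0.258 | 0.240 | 0.217 |
| 0.30 | about 0.60 | 0.447 | 0.411 | 0.368 |
| 0.38 | about 0.80 | 0.620 | 0.579 | 0.515 |
| 0.50 | about 0.96 | 0.848 | 0.806 | 0.735 |

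The continuous term does better throughout, but reaches 80% power only at a correlation of about 0.38. Nothing in the documents supports or excludes that value.

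**The case against.** The strongest reply is that the two-group contrast is the question the trial set itself. It appears as an objective, an endpoint and hypothesis B, and Section 1.7 gives a reason for the 20% line: expected benefit may differ in those who could not lose weight with surgery. Group means and SDs also feed directly into planning the later trial, which Section 1.31 names as a use of these data. This stands. It rules out replacing the comparison with a slope, but not adding one.

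The second reply is that the efficiency loss is conditional, which also stands. Normality is open to doubt because only patients who still have obesity after surgery are eligible, so some of the best surgical responders are absent. If the true relation is a step at 20%, the cut loses little and a linear term may miss it.

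Several stronger readings are tempting and are not supported:
- A reader might infer that the cut discards a known fraction of the information in this trial. The fraction depends on a split and a shape that the documents do not give.
- A reader might blame the cut for the large detectable difference. Most of it comes from having about 40 participants, since the slope still needs about 2.2 to 2.4 kg/m².
- A reader might say that the plan concedes inadequate power here. Section 1.31 only declines to assume adequacy. The statement in Section 1.33.7 that the sample is too small concerns age, sex and race/ethnicity subgroups.
- A reader might take the 26% reduction in Section 1.4 as this trial's expected value, close to the cut. It is a three-year result from a cited cohort, not a nadir value or a forecast for these participants.
- A reader might stress that errors in past BMI values move people across 20%. The documents give no error size, and the same errors would also flatten a fitted slope.

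**Conclusion.** The point holds as a modest, inexpensive improvement and not as an error in the plan. Surgical response is analysed only as a two-level factor although the percentage behind it is needed to form the groups. Under a normal predictor and a linear relation, the cut loses about 36% of the information at 50:50, 51% at 20:80 and 66% at 10:90; under a step at 20% it loses little. For BMI the slope lowers the detectable contrast from about 2.7 to 3.5 kg/m² to about 2.2 to 2.4 kg/m² over splits from 20:20 to 8:32. That is a real gain, but it does not give the comparison adequate power for an effect of the size the plan assumes overall. The kg/m² figures use an SD taken from one-year data. A different 16-week SD would rescale them in proportion and leave the relative efficiency unchanged.

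**What to change.** Keep the 20% group comparison in Section 1.33.3 as the stated analysis for this objective. Prespecify beside it, for both BMI and fat mass, a linear model of the week-16 change on percentage BMI reduction at nadir as a continuous term, with the same candidate covariates (sex, race, age, height). Report the slope with a 95% CI and a simple check for non-linearity, such as a quadratic term or a smoothed plot. Report the observed number on each side of 20% and the distribution of the percentage.

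Adjustment for baseline BMI should be a sensitivity analysis at most. Post-surgical BMI may be related to surgical response, so including it would change what the slope means.

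The cost is one further analysis per outcome on data the trial already needs, with no change to visits, eligibility or treatment. A linear term can miss a true step at 20%, which the retained group comparison covers.

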Visits 2-4: Each participant will undergo a brief history and directed physical examination to include injection site examination at monthly visits. Weight, height, and blood pressure will be measured at each visit. All participants will be assessed for adverse effects of study drug. Female participants will undergo a repeat pregnancy test at every visit. All participants will meet with Nutrition Staff to receive standardized education on a healthy diet. Used 1-month supply of liraglutide pens will be returned to research team and new 1-month supply of liraglutide will be provided to participant. At visit 4, a wrist accelerometer to measure free living physical activity will be placed and testing on attention bias to highly palatable images will be conducted. They will also receive material to collect stool at home if they choose to turn in stool samples at Visit 5.

Visit 5 (at ~16 weeks): Each participant will undergo a history and physical examination and female participants will undergo a pregnancy test. All participants will then undergo fasting blood work followed by 2-hour oral glucose tolerance testing, questionnaires, testing on appetite, DXA scan, and energy intake measurement at a buffet meal at the NIH Clinical Center. They will meet with Nutrition Staff to review their 1-week food log and receive standardized education on a healthy diet and physical activity. Each participant will have the option to turn in stool samples collected at home or during their clinic visit. Used 1-month supply of liraglutide pens will be returned to research team. Liraglutide will be discontinued at this visit. The wrist accelerometer will be returned.

Visit 6 (off medication, at ~28 weeks): Each participant will undergo a history and physical examination. Weight, height, and waist circumference will be measured.

Abbreviated Title: Liraglutide in Teens Post-SG

Version Date: 1/30/23

INTRODUCTION

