1.26 EFFICACY ASSESSMENTS

1.26.1 Clinical Evaluations

Physical examination: Participant's height (on a calibrated stadiometer), weight (on a calibrated scale), waist circumference (using a non-stretching tape measure), and vital signs (temperature, pulse, respirations, blood pressure) will be measured. A complete physical examination (including review of peripheral lymph nodes, head, eyes, ears, nose, mouth and oropharynx, neck, heart, lungs, abdomen, musculoskeletal, extremities, neurologic, skin, and Tanner staging) will be performed at Visit 1 and 6. At other visits, a symptom-directed history and physical examination will be done. At all visits, participant's height (in cm), weight (in kg), and vital

Abbreviated Title: Liraglutide in Teens Post-SG

Version Date: 1/30/23

signs will be measured. Body mass index (BMI, kg/m²) will be calculated and used to determine BMI-SDS according to the Centers for Disease Control standards for age and sex [3]). Subjects will rest for 5 minutes in the seated position with the antecubital fossa supported at heart level when blood pressure measurements are made.

Imaging assessment: The participant will undergo a DXA scan at Visit 1 and 5. The participant will lie on a flat table with the x-ray source below the table and the detector above. Participants will undergo DXA scans in the Metabolic Clinical Research Unit (MCRU) using the Lunar iDXA (GE Healthcare, Madison, WI, USA) machine. The scan takes approximately 5-10 minutes. An external standard, simulating bone, fat, and muscle, is scanned once a week to validate measurements. This standard allows calculation of total body fat, muscle, and bone mass, and percentage of body fat. For the iDXA scan used in this study, the total effective dose of radiation from the two scans performed is 0.00006 rem, which is below the guideline of 5 rem (for adults) and 0.5 rem (for children) per year allowed for research subjects by the NIH Radiation Safety Committee.

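### LOCF is the main missing-data method for the secondary BMI change on grounds of sample size, overlooking a repeated-measures model that imputes nothing and fits about 43 participants; the gain is negligible at the planned loss and grows with it

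*Combined protocol and SAP*

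**What the plan says.** Section 1.33.3 places the key secondary analyses in the ITT dataset: "They will be calculated as changes from baseline to 16-week visit in the ITT dataset". The within-group test uses two time points: "Changes in BMI and fat mass after 16 weeks of liraglutide will be evaluated using paired t-tests of baseline versus 16-week values". The poor-versus-typical responder comparison is an ANCOVA on the same change.

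For missing values, "For these analyses, last observation carried forward (LOCF) imputation will be used for missing data". The reason given is "The sample is too small to use any other statistical imputation method accurately". The only sensitivity analysis is a second single imputation: "A sensitivity analysis using baseline observation carried forward (BOCF) will also be conducted".

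The Schedule of Activities (1.3) has height and weight taken throughout. For Visits 2 to 4 its summary says "Weight, height, and blood pressure will be measured at each visit", and 1.26.1 repeats this for all visits. BMI is therefore available at Days 0, 28, 56, 84 and 112. Fat mass is different: "The participant will undergo a DXA scan at Visit 1 and 5". No mixed model or other likelihood-based repeated-measures analysis appears anywhere in the plan.

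**The concern.** LOCF treats a participant's last recorded BMI as if it had been measured at week 16. Visit 2 (Day 28) falls about when the titration steps in Table 1 (1.17.2.1) end, so a value carried from there mostly reflects titration. While BMI is still falling, such a value understates what that participant would have lost. Early changes also vary less than week-16 changes, so the filled dataset has too small an SD and the interval looks more precise than it should.

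The stated reason covers imputation methods only. It passes over an analysis that needs no imputation and can use three on-treatment BMI measurements (Visits 2 to 4) that the paired t-test ignores. At stake are the reported week-16 mean change and its confidence interval, tested at one-sided 5% (1.33.1).

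**Working it through.** **The plan's own figures.** Section 1.31 takes a change of -1.39 kg/m² with SE 0.31 and n = 125.
- SD = 0.31 × √125 = 3.466 (plan: 3.46); dz = 1.39/3.46 = 0.4017.
- A one-sided 0.05 paired t-test with N = 40 has power 0.803, so the stated 80% reproduces.
- Planned loss: 6/125 = 4.8% off treatment by week 16 in the cited adolescent trial; 3/43 = 7.0% if 40 of 43 complete.

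**Assumptions not in the documents.** Loss is random and spread evenly after Visits 2, 3 and 4. Two paths to -1.39 at week 16 are used:
- Linear: changes at weeks 4, 8 and 12 of -0.3475, -0.695, -1.0425; variance proportional to time.
- Decelerating: -0.5, -0.9, -1.2; SDs 1.2, 2.0, 2.8.

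**Bias of LOCF in the mean** = loss rate × average shortfall of the carried value.
- Linear: (1.0425 + 0.695 + 0.3475)/3 = 0.695.
- Decelerating: (0.89 + 0.49 + 0.19)/3 = 0.523.

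| Loss | Linear | Decelerating |
|---|---|---|
| 5% | 0.035 | 0.026 |
| 7% | 0.049 | 0.037 |
| 20% | 0.139 | 0.105 |

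All are in kg/m², towards a smaller BMI loss. Simulated random-loss values ran from 0.02 at 5% to 0.15 at 20%, with Monte Carlo error of 0.01 to 0.04.

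**SD after LOCF** = √(weighted within-visit variance + variance between the visit means). At 20% loss:
- Linear: mean early variance 11.97 × (0.25 + 0.50 + 0.75)/3 = 5.99; 0.8 × 11.97 + 0.2 × 5.99 = 10.77; plus 0.09 gives SD 3.30.
- Decelerating: (1.44 + 4.00 + 7.84)/3 = 4.43; 0.8 × 11.97 + 0.2 × 4.43 = 10.46; plus 0.06 gives SD 3.24.

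At 5% loss the same formula gives 3.42 and 3.41. With 43 participants and 20% loss, the linear path yields an SE of 3.30/√43 = 0.503. Had all 43 been observed it would be 3.46/√43 = 0.528. LOCF thus reports more precision with nine values missing than with none.

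**Can the model be fitted?** An unstructured covariance over four visits has 4 × 5/2 = 10 parameters. Simulated at n = 43:
- Linear path, maximum likelihood, losses of 5, 10 and 20%: no failures in 9,000 fits; means -1.38 to -1.43.
- Decelerating path, REML, losses of about 5 and 20%: every fit converged. SD at 20% random loss was 3.38, against 3.18 for LOCF.

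**Other loss mechanisms** (decelerating path, 20% loss, Monte Carlo SE about 0.04; negative means the loss is overstated):

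| Mechanism | LOCF | Mixed model | BOCF |
|---|---|---|---|
| Poor responders leave, missing at random | -0.01 | -0.04 | -0.13 |
| Not missing at random | -0.13 | -0.20 | -0.20 |

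**Fat mass.** With DXA at Visits 1 and 5 only, the last observation before a missing Visit 5 scan is the baseline scan. LOCF and BOCF are then the same analysis.

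**The case against.** Much of the opposing case stands.

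- *Size at the planned loss.* A bias of 0.049 against an SE near 0.52 is under a tenth of a standard error. Across all the loss mechanisms simulated at 5 to 7%, it was at most about 0.08 kg/m².
- *Total error.* LOCF had the lower root-mean-square error in all 16 simulated settings (linear path, random loss: 0.52 against 0.53 at 5%, 0.52 against 0.56 at 20%), with similar interval coverage. Part of this is shrinkage: √(0.139² + 0.503²) = 0.52. It still means the mixed model is not better on every criterion.
- *Missing data may be rarer than stopping drug.* The 95% in 1.31 is an on-treatment figure, and 1.17.2.3 and 1.23 seek a Visit 5 return from people who stop. This should limit missing values but cannot guarantee them.
- *The remedy as worded was not simulated.* The runs had no baseline covariate, and no type I error result is available.

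Four stronger readings are tempting and are not supported.
- A reader might infer that the sample-size sentence is false. It speaks of imputation methods, and no other imputation method was tested; it overlooks the mixed model rather than ruling it out.
- A reader might take the 80% success mark in 1.33.2 as a tolerated 20% missing-data rate. That paragraph concerns completion and per-protocol adherence, so 20% here is only an assumption.
- A reader might conclude that LOCF biases the primary effect size. Section 1.33.2 uses the observed mean change and gives no missing-data rule; LOCF is specified only for the secondary analyses.
- A reader might expect the mixed model to remove bias. That holds only under missing at random.

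**Conclusion.** The point holds as a cheap improvement and does not invalidate the planned analysis. LOCF is justified by a reason that does not reach the obvious alternative, and it discards information already collected. Under random loss with BMI still falling, it understates the mean loss by about 0.02 to 0.05 kg/m² at 5 to 7% loss and about 0.10 to 0.15 at 20%. The SD of change comes out at about 3.2 to 3.4 against 3.46.

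These sizes rest on an assumed path, on taking the one-year change of -1.39 as the week-16 value, and on the assumed timing and mechanism of loss. With response-dependent loss the mean bias went either way: on the decelerating path it cancelled, while on the linear path at 20% loss LOCF gave -1.23. The required N does not change. The case for change is strongest if loss exceeds plan, which cannot be known when the SAP is fixed.

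**What to change.** In 1.33.3, for the secondary BMI change:

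1. Make the main analysis a REML mixed model for repeated measures on change at Visits 2 to 5, with visit as a factor, baseline BMI centred at its mean, unstructured covariance and small-sample degrees of freedom. Report the week-16 mean change with its confidence interval.
2. Keep LOCF and BOCF as sensitivity analyses. BOCF brings in ITT members with no post-baseline BMI, whom the model omits (1.32 counts assigned but untreated participants as ITT). It also serves as the conservative check for regain after stopping. State its limit: it is conservative only if those lost did not end above baseline, and in the poor-responder settings above it overstated the loss.
3. Replace the sample-size sentence with one saying that the model uses all observed visits without imputation and assumes missing at random.
4. State that for fat mass LOCF and BOCF are identical, so the repeated-measures model does not apply and the planned sensitivity analysis adds nothing.

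The cost is SAP wording and modest extra analysis. The interval is about 2% wider at 5% loss and about 11% wider at 20% (0.56/0.503 = 1.11), and the result relies on missing at random. The change does not cover the ANCOVA between responder groups.
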